9.2 Adverse Events

An adverse event (AE) is any untoward medical occurrence that occurs in conjunction with the use of a medicinal product in humans, whether or not considered to have a causal relationship to the medicinal product. An AE can, therefore, be any unfavorable or unintended sign (including a clinically significant abnormal laboratory finding), symptom, or disease

temporally associated with the use of a medicinal product, whether or not considered related to the medicinal product.

Adverse event data will be integrated, listed, and summarized for the Safety population. Events will be presented according to MedDRA® system organ class (SOC) and preferred term (PT). Summaries will be ordered alphabetically by SOC and PT, and by decreasing frequency of preferred term among all treatment/analysis groups regardless of whether a "total" column is presented.

Partial (Incomplete) AE onset and end dates will be listed as such. All AEs collected on the AE eCRF page will be considered treatment–emergent.

Most commonly reported (at least 2% of either active or placebo treatments) AEs will be presented by preferred term, and summarized by treatment/analysis group.

For each summary, at each of the SOC and PT levels, a subject will be counted once if he/she reported one or more AEs. Percentages will be calculated out of the number of subjects in the Safety population.

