9.2.8 Adverse Events of Special Interest

Adverse events of special interest are grouped into three event categories: Neuropsychiatric (CNS), Falls, and Hallucinations. The CNS category combines the following SOCs: Nervous system disorder and Psychiatric disorder. The Falls category combines all PTs that contain the term "Fall" or "Falls". The Hallucinations category combines all PTs that contain the term "Hallucination".

Event incidence will be summarized treatment/analysis group.

Time to onset will be analyzed and is defined as the number of days from the first dose of study drug to the onset of the first AE in the category. Subjects will be censored at the latest date known not to have had such AE. The median time to event and the associated 95% confidence interval for the Placebo and 340 mg ADS-5102 treatment groups will be estimated using the Kaplan-Meier method. Kaplan-Meier estimates of the survival function will be calculated and displayed graphically.

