Safety Population

Repeat of 1.6.1.2

Columns:

- 1. < median
- 2. ≥ median

Note: A subject is counted once for each type of event. Percentages are calculated out of the number of subjects in each subgroup category for the given treatment.

Source Data: Listing 2.6.1

Table 1.6.1.11
Overview of Adverse Events by Age at PD Diagnosis
Safety Population

Repeat of 1.6.1.2

Columns:

- 1. < median
- 2. ≥ median

Note: A subject is counted once for each type of event. Percentages are calculated out of the number of subjects in each subgroup category for the given treatment. Source Data: Listing 2.6.1

<DIRECTORY PATH>PROGRAM NAME Executed: DDMMMYYYY hh:mm

Table 1.6.1.12

Overview of Adverse Events by Prior Deep Brain Stimulation Safety Population

Repeat of 1.6.1.2

Columns:

- 1. Yes
- 2. No

Note: A subject is counted once for each type of event. Percentages are calculated out of the number of subjects in each subgroup category for the given treatment. Source Data: Listing 2.6.1

Table 1.6.1.13 Overview of Adverse Events by Geographic Region Safety Population

Repeat of 1.6.1.2

Columns:

- 1. European Union
- 2. North America

Note: A subject is counted once for each type of event. Percentages are calculated out of the number of subjects in each subgroup category for the given treatment.

Source Data: Listing 2.6.1

 $\begin{array}{c} \text{Table 1.6.2.1} \\ \text{Adverse Events, by System Organ Class and Preferred Term} \\ \text{Safety Population} \end{array}$

System Organ Class Preferred Term	Placebo (N=xx) n (%)	340mg ADS-5102 (N=xx) n (%)	≥340mg ADS-5102 (N=xx) n (%)	ADS-5102 (N=xx) n (%)
Number (%) of subjects with any AEs	xx (xx.x)	xx (xx.x)	xx (xx.x)	xx (xx.x)
System Organ Class 1	xx (xx.x)	xx (xx.x)	xx (xx.x)	xx (xx.x)
Preferred Term 1	xx (xx.x)	xx (xx.x)	xx (xx.x)	xx (xx.x)
Preferred Term 2	xx (xx.x)	xx (xx.x)	xx (xx.x)	xx (xx.x)
Preferred Term 3	xx (xx.x)	xx (xx.x)	xx (xx.x)	xx (xx.x)
System Organ Class 2	xx (xx.x)	xx (xx.x)	xx (xx.x)	xx (xx.x)
Preferred Term 1	xx (xx.x)	xx (xx.x)	xx (xx.x)	xx (xx.x)
Preferred Term 2	xx (xx.x)	xx (xx.x)	xx (xx.x)	xx (xx.x)
Preferred Term 3	xx (xx.x)	xx (xx.x)	xx (xx.x)	xx (xx.x)

Note: A subject is sounted once within

Note: A subject is counted once within each preferred term and system organ class. Percentages are calculated out of the number of subjects in each treatment/analysis group. AEs are coded using MedDRA Version 17.0.

Source Data: Listing 2.6.1

Table 1.6.2.2

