xxxxx-xx-xxx	XXXXX	340mg ADS-5102	XXXXXXXXXXXXXXXXXXXXXXXXXXXXXXXXXXXXXX	DDMMMYYYY (xx)/ DDMMMYYYY (xx)/ XX	Moderate/ Related/ Recovered/Resolved with sequelae/ Drug Interrupted
xxxxx-xx-xxx	XXXXX	340mg ADS-5102	XXXXXXXXXXXXXXXXXXXXXXXXXXXXXXXXXXXXXX	DDMMMYYYY (xx)/ DDMMMYYYY (xx)/ XX	Severe/ Not Related/ Unknown/ Drug Withdrawn
xxxxx-xx-xxx	XXXXX	260mg ADS-5102	XXXXXXXXXXXXXXXXX/ XXXXXXXXXXXXXXXX/ XXXXXX	DDMMMYYYY (xx)/ DDMMMYYYY (xx)/ XX	Mild/ Related/ Not Recovered/Not resolved/ Other
XXXXX-XX-XXX	XXXXX	340mg ADS-5102	XXXXXXXXXXXXXXXXXXXXXXXXXXXXXXXXXXXXXX	DDMMMYYYY (xx)/ DDMMMYYYY (xx)/ XX	Severe/ Not Related/ Fatal/ Dose not changed

¹Duration (Days) = Stop date - Start date + 1.

Source Data: Listing 2.6.1

<DIRECTORY PATH>PROGRAM NAME Executed: DDMMMYYYY hh:mm

Adverse Events Leading to Study Drug Discontinuation, by System Organ Class and Preferred Term Safety Population

Same display as 1.6.2.1

Note: A subject is counted once within each preferred term and system organ class. Percentages are calculated out of the number of subjects in each treatment/analysis group. AEs are coded using MedDRA Version 17.0.

Source Data: Listing 2.6.3

<DIRECTORY PATH>PROGRAM NAME Executed: DDMMMYYYY hh:mm

Table 1.6.8

Adverse Events Leading to Study Drug Dose Reduction, by System Organ Class and Preferred Term Safety Population

Same display as 1.6.2.1

Note: A subject is counted once within each preferred term and system organ class. Percentages are calculated out of the number of subjects in each treatment/analysis group. AEs are coded using MedDRA Version 17.0.

Source Data: Listing 2.6.3

Table 1.6.9 Listing of Adverse Events Leading to Death Safety Population

Same display as 1.6.6, with outcome "Death".

¹Dur = Duration (Days = Stop date - Start date + 1). Source Data: Listing 2.6.1

Table 1.6.10.1
Incidence of AE (Neuropsychiatric)
Safety Population

System Organ Class		340mg	≥340mg	
Preferred Term	Placebo	ADS-5102	ADS-5102	ADS-5102
Number of AE (Neuropsychiatric) events	XX	XX	XX	XX
System Organ Class 1	XX	XX	XX	XX
Preferred Term 1	xx	XX	XX	XX
Preferred Term 2	xx	XX	XX	XX
Preferred Term 3	xx	XX	XX	XX
	XX	XX	XX	XX
	xx	XX	XX	XX
System Organ Class 2	xx	XX	XX	XX
Preferred Term 1	xx	XX	XX	XX
Preferred Term 2	XX	XX	XX	XX
Preferred Term 3	xx	XX	XX	XX

Note: The Neuropsychiatric category combines the following System Organ Classes: Nervous system disorder and Psychiatric disorder. AEs are coded using MedDRA Version 17.0.

Source Data: Listing 2.6.1

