Table 1.6.10.2

Kaplan-Meier Analysis of Time to Onset of AE (Neuropsychiatric)

Safety Population

	Placebo	340 mg ADS-5102
	(N=xx)	(N=xx)
Days to onset of first AE: Neuropsychiatric		
Event n(%)	xx (xx.x)	xx (xx.x)
10th percentile (days)	XX.X	XX.X
25 th percentile (days)	XX.X	XX.X
50th percentile (days)	XX.X	XX.X
75 th percentile (days)	XX.X	XX.X
90th percentile (days)	XX.X	XX.X
Min - Max	xx.x - xx.x	xx.x - xx.x
edian (days)		
Estimate	XX.X	XX.X
95% CI	x.xx, x.xx	x.xx, x.xx

Note: Percentages are calculated out of the number of subjects in each treatment group. "+" in MIN - MAX means censored value. AEs are coded using MedDRA Version 17.0. NE = Non-estimable.

Note: The Neuropsychiatric category combines the following System of Organs: Nervous system disorder and Psychiatric disorder. Subjects will be censored at their last contact date if no AE (Neuropsychiatric) occurred.

Source Data: Listing 2.6.1

<DIRECTORY PATH>PROGRAM NAME Executed: DDMMMYYYY hh:mm

Programming Note: Some percentiles will be non-estimable. When this occurs, use " NE^{1} "

Table 1.6.10.3

Kaplan-Meier Analysis of Time to Onset of AE (Neuropsychiatric) by Gender Safety Population

	Placebo	340 mg ADS-5102
	(N=xx)	(N=xx)
Days to onset of first AE: Neuropsychiatric		
Event n(%)	xx (xx.x)	xx (xx.x)
10th percentile (days)	XX.X	xx.x
25 th percentile (days)	XX.X	xx.x
50th percentile (days)	XX.X	xx.x
75 th percentile (days)	XX.X	xx.x
90 th percentile (days)	XX.X	XX.X
Min - Max	xx.x - xx.x	xx.x - xx.x
Median (days)		
Estimate	XX.X	XX.X
95% CI	X.XX, X.XX	x.xx, x.xx

Note: Percentages are calculated out of the number of subjects in each treatment group. "+" in MIN - MAX means censored value. AEs are coded using MedDRA Version 17.0. NE = Non-estimable.

Note: The Neuropsychiatric category combines the following System of Organs: Nervous system disorder and Psychiatric disorder. Subjects will be censored at their last contact date if no AE (Neuropsychiatric) occurred.

Source Data: Listing 2.6.1

<DIRECTORY PATH>PROGRAM NAME Executed: DDMMMYYYY hh:mm

Programming Note: Some percentiles will be non-estimable. When this occurs, use " NE^{1} "

Gender: Male

Min - Max

340 mg ADS-5102 (N=xx)

> xx (xx.x) xx.x

> > XX.X

XX.X

XX.X

XX.X

xx.x - xx.x

XX.X

XX.X

XX.X

xx.x - xx.x

Table 1.6.10.3

Kaplan-Meier Analysis of Time to Onset of AE (Neuropsychiatric) by Gender Safety Population

	Placebo
	(N=xx)
Days to onset of first AE: Neuropsychiatric	
Event n(%)	xx (xx.x)

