Kaplan-Meier Analysis of Time to Onset of AE (Neuropsychiatric) by Geographic Region Safety Population

Repeat of 1.6.10.3

Geographic Region:

- 1. European Union
- 2. North America

Note: Percentages are calculated out of the number of subjects in each treatment group. "+" in MIN - MAX means censored value. AEs are coded using MedDRA Version 17.0. NE = Non-estimable.

Note: The Neuropsychiatric category combines the following System of Organs: Nervous system disorder and Psychiatric disorder. Subjects will be censored at their last contact date if no AE (Neuropsychiatric) occurred.

Source Data: Listing 2.6.1

Table 1.6.11.1
Incidence of AE (Falls)
Safety Population

Repeat of 1.6.10.1

Note: Percentages are calculated out of the number of subjects in each treatment group. "+" in MIN - MAX means censored value. AEs are coded using MedDRA Version 17.0. NE = Non-estimable.

Note: The Falls category combines all Preferred Terms that contain the terms "Fall" or "Falls". Subjects will be censored at their last contact date if no AE (Falls) occurred.

Source Data: Listing 2.6.1

<DIRECTORY PATH>PROGRAM NAME Executed: DDMMMYYYY hh:mm

Table 1.6.11.2

Kaplan-Meier Analysis of Time to Onset of AE (Falls)

Safety Population

Repeat of 1.6.10.2

Note: Percentages are calculated out of the number of subjects in each treatment group. "+" in MIN - MAX means censored value. AEs are coded using MedDRA Version 17.0. NE = Non-estimable.

Note: The Falls category combines all Preferred Terms that contain the terms "Fall" or "Falls". Subjects will be censored at their last contact date if no AE (Falls) occurred.

Source Data: Listing 2.6.1

<DIRECTORY PATH>PROGRAM NAME Executed: DDMMMYYYY hh:mm

Programming Note: Some percentiles will be non-estimable. When this occurs, use " $NE^{1/7}$

Kaplan-Meier Analysis of Time to Onset of AE (Falls) by Gender Safety Population

Repeat of 1.6.10.3

Gender:

- 1. Female
- 2. Male

Note: Percentages are calculated out of the number of subjects in each treatment group. "+" in MIN - MAX means censored value. AEs are coded using MedDRA Version 17.0. NE = Non-estimable.

Note: The Falls category combines all Preferred Terms that contain the terms "Fall" or "Falls". Subjects will be censored at their last contact date if no AE (Falls) occurred.

Source Data: Listing 2.6.1

<DIRECTORY PATH>PROGRAM NAME Executed: DDMMMYYYY hh:mm

Table 1.6.11.4

Kaplan-Meier Analysis of Time to Onset of AE (Falls) by Age Safety Population

Repeat of 1.6.10.3

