Note: Percentages are calculated out of the number of subjects in each treatment group. "+" in MIN - MAX means censored value. AEs are coded using MedDRA Version 17.0. NE = Non-estimable.

Note: The Falls category combines all Preferred Terms that contain the terms "Fall" or "Falls". Subjects will be censored at their last contact date if no AE (Falls) occurred.]

Source Data: Listing 2.6.1

Kaplan-Meier Analysis of Time to Onset of AE (Falls) by Prior Deep Brain Stimulation Safety Population

Repeat of 1.6.10.3

Prior Deep Brain Stimulation:

- 1. Yes
- 2. No

Note: Percentages are calculated out of the number of subjects in each treatment group. "+" in MIN - MAX means censored value. AEs are coded using MedDRA Version 17.0. NE = Non-estimable.

Note: The Falls category combines all Preferred Terms that contain the terms "Fall" or "Falls". Subjects will be censored at their last contact date if no AE (Falls) occurred.

Source Data: Listing 2.6.1

<DIRECTORY PATH>PROGRAM NAME Executed: DDMMMYYYY hh:mm

Table 1.6.11.14

Kaplan-Meier Analysis of Time to Onset of AE (Falls) by Geographic Region Safety Population

Repeat of 1.6.10.3

Geographic Region:

- 1. European Union
- 2. North America

Note: Percentages are calculated out of the number of subjects in each treatment group. "+" in MIN - MAX means censored value. AEs are coded using MedDRA Version 17.0. NE = Non-estimable.

Note: The Falls category combines all Preferred Terms that contain the terms "Fall" or "Falls". Subjects will be censored at their last contact date if no AE (Falls) occurred.

Source Data: Listing 2.6.1

Table 1.6.12.1 Incidence of AE (Hallucinations) Safety Population

Repeat of 1.6.10.1

Note: Percentages are calculated out of the number of subjects in each treatment group. "+" in MIN - MAX means censored value. AEs are coded using MedDRA Version 17.0. NE = Non-estimable.

Note: The Hallucinations category combines all Preferred Terms that contain the term "Hallucination". Subjects will be censored at their last contact date if no AE (Hallucinations) occurred.

Source Data: Listing 2.6.1

<DIRECTORY PATH>PROGRAM NAME Executed: DDMMMYYYY hh:mm

1.6.12.2

Kaplan-Meier Analysis of Time to Onset of AE (Hallucinations)

Safety Population

Repeat of 1.6.10.2

Note: Percentages are calculated out of the number of subjects in each treatment group. "+" in MIN - MAX means censored value. AEs are coded using MedDRA Version 17.0. NE = Non-estimable.

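### The three special-interest incidence shells print event counts, without N or percentages, where SAP 9.2 calls for subjects counted once with percentages

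*SAP*

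**What the plan says.** SAP 9.2 gives the counting rule for adverse event outputs: "For each summary, at each of the SOC and PT levels, a subject will be counted once if he/she reported one or more AEs". The denominator follows: "Percentages will be calculated out of the number of subjects in the Safety population". SAP 6 is consistent with this, since it summarizes categorical data by number and percentage of subjects.

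SAP 9.2.8 defines the Neuropsychiatric, Falls and Hallucinations categories. On incidence it says only "Event incidence will be summarized treatment/analysis group", and it writes no exception to 9.2.

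The shell for Table 1.6.10.1 is titled as an incidence table and laid out by SOC and PT. Its first row is "Number of AE (Neuropsychiatric) events". Every cell is a bare placeholder, and the four column headers carry no N. The shells for Tables 1.6.11.1 (Falls) and 1.6.12.1 (Hallucinations) each read "Repeat of 1.6.10.1". Under both stands the note "Percentages are calculated out of the number of subjects in each treatment group", followed by explanations of a plus sign for censored values and of NE.

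The main SOC and PT shell, Table 1.6.2.1, does follow 9.2: its first row is "Number (%) of subjects with any AEs" and each column has an N.

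**The concern.** A programmer working from SAP 9.2 and one working from the shell would produce different tables, and the footnotes under two of the shells do not describe the layout above them.

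If the shell is followed, the tables set raw counts side by side for groups that differ greatly in size and follow-up. A single subject with many falls is then indistinguishable, within that table, from many subjects with one fall each. The integrated summary plans no formal testing, so its descriptive tables are the analysis, and these are the categories that the sponsor singled out.

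**Working it through.** **Text against shell.** The plan states no figure to reproduce, so the first check sets the places side by side.

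| Place in SAP | Unit counted | N in header | Percentages |
|---|---|---|---|
| 9.2 text | subjects, once per SOC/PT | – | of Safety population |
| 9.2.8 text | event incidence, not defined further | – | not stated |
| Table 1.6.10.1 shell | events | no | no |
| Tables 1.6.11.1 and 1.6.12.1 shells | events, by repetition | no | none in layout; footnote says yes |
| Table 1.6.2.1 shell | subjects | yes | yes |

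This does not come from text extraction. The row label itself names events, and neighbouring shells keep both N and the percentage pattern.

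**What other tables supply.**

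- Table 1.6.10.2, under "Days to onset of first AE: Neuropsychiatric", prints N and the number and percentage of subjects with an event. Tables 1.6.11.2 and 1.6.12.2 repeat it for Falls and Hallucinations. All three cover Placebo and 340 mg only.
- Table 1.6.2.1 gives subject n (%) for each SOC and PT in all four columns, so the term Fall is there.
- Not found in any planned table: subjects with any Neuropsychiatric or any Hallucination event, for ≥340 mg and pooled ADS-5102. Adding SOC or PT rows does not give it, because one subject can appear in several.

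**Size of that gap.** SAP 3 gives 83 AM201 subjects in four equal arms for 8 weeks: 83 / 4 = 20.75, taken as 21 per arm. Beyond 340 mg, the ≥340 mg column adds the 420 mg arm (21 subjects, 21 × 8 = 168 subject-weeks). The pooled column adds the 260 mg arm as well (42 subjects, 336 subject-weeks). Taking the Kaplan-Meier event count at 340 mg as X, the missing count lies between X and X + 21 for ≥340 mg, and between X and X + 42 for pooled.

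For percentages, assume 84 subjects (21 + 63) at 340 mg from the randomized studies, 100 to 250 from PD302, and no overlap between studies:

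- ≥340 mg: 21 / (84 + 100 + 21) = 10.2 percentage points, down to 21 / (84 + 250 + 21) = 5.9.
- Pooled: 42 / (84 + 100 + 42) = 18.6 percentage points, down to 42 / (84 + 250 + 42) = 11.2.

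These are ceilings on the width of the uncertainty.

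**Why raw counts cannot be compared across columns (illustration only).** Assume equal arms and full completion of the randomized studies. Placebo exposure is then 21 × 8 + 63 × 25 = 1,743 subject-weeks. The 340 mg column has the same plus PD302. With identical event rates, the ratio of counts is the ratio of exposure:

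- PD302 100 subjects × 20 weeks: 3,743 / 1,743 = 2.1
- PD302 200 × 40: 9,743 / 1,743 = 5.6
- PD302 250 × 101, full enrolment and full treatment: 26,993 / 1,743 = 15.5

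At an assumed 0.5 events per subject-year, the middle case prints 1,743 / 52.18 × 0.5 = 16.7 events on placebo and 9,743 / 52.18 × 0.5 = 93.4 at 340 mg.

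**Whether subject percentages cure this.** Only in part. At the same constant rate, the chance of at least one event is 1 − exp(−0.5 × weeks / 52.18): 7.4% over 8 weeks, 21.3% over 25 and 31.8% over 40. Placebo: (21 × 0.074 + 63 × 0.213) / 84 = 18%. The 340 mg column, with 200 PD302 subjects and no overlap: (21 × 0.074 + 63 × 0.213 + 200 × 0.318) / 284 = 28%. Unequal follow-up still separates two groups with the same rate.

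**The case against.** The strongest reply is that little is lost. 340 mg is the proposed dose and Placebo the only control, and for both the Kaplan-Meier tables print the subject count and handle differing follow-up. N can be read from neighbouring tables with the same columns. Listing 2.6.1 holds every event by subject, so any category count can be derived. SAP 7.2 refers readers to the AM201 results for the 260 mg and 420 mg doses. This stands, and it limits the consequence to two columns that nearly duplicate the 340 mg column.

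A second reply is that event counts were intended, because 9.2.8 speaks of event incidence and the shell row says events. That reading is possible. But 9.2 covers each summary, 9.2.8 claims no exemption, and two of the three footnotes speak of percentages of subjects. The SAP does not settle the matter, which is itself a reason to correct it.

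A reader might infer something stronger: that the plan would overstate risk at 340 mg against placebo by up to 15-fold, or that nobody could tell how many subjects fell or hallucinated. The documents do not support either. The comparison of 340 mg with placebo has subject counts elsewhere, and the 15.5 ratio needs all 250 PD302 subjects to finish 101 weeks before a database freeze whose date is not given.

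**Conclusion.** The inconsistency is real: three tables titled as incidence are drawn as event counts without N or percentages, contrary to SAP 9.2, and two carry footnotes for content that they do not contain. Severity is low. The only summary figure that the plan fails to produce is subject n (%) for any Neuropsychiatric and any Hallucination event in the ≥340 mg and pooled ADS-5102 columns. At most about 21 and 42 AM201 subjects separate those columns from 340 mg, given near-equal AM201 arms and a Kaplan-Meier event count that equals the category count. For Falls, the conclusion that nothing is missing holds as far as the category rests on the single term Fall; the SAP does not list the matching terms.

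The exposure ratios show why raw counts should not be read across columns. They do not measure harm done by the plan, since they rest on assumed PD302 enrolment and mean follow-up and their top value is a ceiling. No test, estimate or decision rule changes.

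**What to change.** Redraw the shells for Tables 1.6.10.1, 1.6.11.1 and 1.6.12.1 with (N=xx) and n (%) in each of the four column headers. Make the first row the number (%) of subjects with any event in the category, followed by SOC and PT rows as n (%). Replace the Kaplan-Meier footnotes under the Falls and Hallucinations shells with ones that describe the table.

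If event counts are kept, show them beside events per 100 subject-years, because subject percentages alone leave the difference in follow-up. Take exposure from the same studies as the events. Table 1.5 as noted would not match, since for subjects with a treatment gap it uses PD302 only, while SAP 9 includes all available safety data from first dose.

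The cost is three shells and their footnotes. The subject-counting code for Table 1.6.2.1 can be reused with a category flag. No new data, tables or category definitions are needed.
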